3.15.1.8 GI Daily Diary Card

As discussed in Section 5.5.1 of the study protocol, participants will fill out a diary card during screening, DEP, and RWP to allow for enhanced capture of the gastrointestinal (GI) AEs. This diary will contain the GI event description start/stop date and the question “*how much did this event bother you?*” with the response being a 0–10-point numeric rating scale with 0 bothered” and 10 bothered”. When the investigator records this event as an AE, the following summaries of the tolerability will be performed:

- For GI TEAEs with a start date in the Screening Period, the tolerability will be summarized by PT and overall.
- For GI TEAEs with a start date in the DEP, the tolerability will be summarized by PT and overall, for each iTD and overall.
- For GI TEAEs with a start date in the RWP, the tolerability will be summarized by PT and overall, for treatment group, and with the active arm, for each iTD and overall.

Note: the other information provided in the GI Daily Diary Card will be incorporated in the adverse event database. For AEs occurring over multiple days, the highest bothersomeness score will be recorded. Should the investigator determine that the event recorded on the daily diary card is not an adverse event, the corresponding GI Daily Diary card entry, including the bothersomeness data, will not be recorded in the adverse event database.

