### 3.2. Dosing and Dose Escalation

SYNBI934v1 will be taken with a meal throughout the study. Participants will take a proton pump inhibitor (PPI) once per day (QD), recommended to occur before breakfast, during all parts of the study (see Section 4.3.4), starting at Day -7 of the DEP. If participants are unable to tolerate the PPI, they may attempt to use an H2 blocker per investigator discretion. If neither the PPI nor H2 blocker can be tolerated, the participant will discontinue from the study.

- Decrease the frequency of dosing for 1 to 2 days. This can be initiated without the approval of the medical monitor.
- Skip dosing 1 to 2 days. This can be initiated without the approval of the medical monitor.
- Skip dosing  $\geq 3$  days. This must be discussed with the medical monitor.
- De-escalate to a previous level after discussion with the medical monitor. In this case, the participant will restart 3 weeks at a previously tolerated dose including its ramp, and this previously tolerated dose will be the iTD. After de-escalation, participants cannot escalate to a higher dose again during Part 1.

In general, a dose is considered intolerable if the participant experiences Grade 3 or more severe TEAEs or Grade 2 GI AEs that do not improve with continued dosing at the same dose level over time. If a dose is de-escalated due to a reason other than Grade 3 or greater or Grade 2 GI TEAEs, or a second de-escalation is required, the medical monitor must be consulted. Participants must take at least 8 of the 9 expected doses on the final 3 days of their iTD period. If not, the medical monitor must be consulted before the participant enters Part 2.

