## 8.10. Safety Analysis

Safety will be evaluated by scheduled monitoring of AEs, vital signs, and clinical laboratory measurements. Safety parameters will be summarized descriptively by the treatment regimen (dose and frequency) that the participant was on at the time of the safety measurement.

By-participant listings of all measurements and parameters will be presented in tabular format, including absolute values and changes from baseline (if applicable), by dose cohort and study day.

Adverse events will be coded using the *Medical Dictionary for Regulatory Activities*, and severity of AEs and laboratory abnormalities will be graded using the National Cancer Institute CTCAE, v5.0, with certain exceptions as listed in [Table 7](#). Adverse events will be tabulated by study period, treatment group, system organ class, and preferred term. Incidence tables of participants with AEs will be presented for all AEs by maximum severity, AESIs, SAEs, AEs assessed as related to IMP, and AEs resulting in discontinuation of study dosing.

For the DEP, safety analyses will be performed on the DEP SAS. For the RWP and OLE study parts, safety analyses will be performed on the corresponding SAS, with results being presented for the responder and nonresponder populations as well as overall population.

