2.2 STUDY DESIGN

This is a 3-part, Phase 3 study consisting of a dose-escalating, open-label period (DEP; Part 1) of up to 15 weeks, followed by a 4-week, double-blind, placebo-controlled, randomized withdrawal period (RWP; Part 2), and an open-label extension (OLE; Part 3) of up to 36 months. [Figure 1](#) presents a study schematic.

In the DEP, all enrolled participants will maintain a stable diet reflecting their baseline Phe intake and receive escalating doses of SYNB1934v1 from approximately 3 to 15 weeks to determine an iTD, which is defined as the highest dose the participant is able to tolerate. A participant will be defined as having reached an iTD if they tolerate 3 weeks at a dose, regardless of whether other doses are tolerated.

Blood Phe level will be measured at each dose level after 3 weeks at that level. A responder will be defined as a participant who achieves a $\geq 20\%$ reduction in blood Phe level compared to DEP baseline on their iTD. For inclusion in the RWP primary efficacy analysis population, response will be assessed at the third week of a participant's established iTD for SYNB1934v1.

If at any time during a 3-week dosing interval in the DEP the participant or investigator considers a dose level to be intolerable, the dose may be de-escalated after discussion with the medical monitor. In this case, the participant will restart 3 weeks at the lower level iTD. After de-escalation, participants cannot escalate to a higher dose again during.

[figure not shown]
The DEP will contain an optional substudy (DEP weekly substudy) to evaluate the range and variability of [REDACTED] at each dose level. The [REDACTED] participants in this substudy will have weekly Phe and Tyr value assessments during the DEP (i.e., with Tyr assessments being primarily assessed for safety).

Once the first [REDACTED] participants have attained an iTD and completed the DEP or the [REDACTED] has a baseline DEP and has been in the study for [REDACTED], whichever occurs earlier, the DEP data will be evaluated by an independent Data Monitoring Committee (DMC). The DMC will use a pre-specified set of criteria based on both safety and efficacy to determine whether the dose regimen is appropriate or whether any doses should be discontinued as well as whether the study should be stopped for futility. Enrollment will not be paused during the interim analysis.

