3.15.1 Adverse Events

Adverse events will be coded using the Medical Dictionary for Regulatory Activities (MedDRA) Version 25.1 (or higher) and will be classified using SOC and PT (with the exception of diarrhea and nausea AEs as discussed in Section 3.15.1.1). Severity of AEs and laboratory abnormalities will be graded using the National Cancer Institute Common Terminology Criteria for Adverse Events. Adverse events causality will be dichotomous: Related or Unrelated (i.e., as defined in Section 6.1.2 of the study protocol).

Treatment emergent adverse events (TEAEs) are any adverse events occurring or worsening in severity after the first administration of SYNB1934v1 study medication.

TEAEs will be tabulated by study Part, treatment group (for Part 2), system organ class, and preferred term. Incidence tables of participants with TEAEs will be presented for all TEAEs by maximum severity, serious AEs (SAEs), TEAEs assessed as related to IMP, and TEAEs resulting in discontinuation of study dosing.

The number and percentage of participants who experienced at least one TEAE as well as the number and percentage of participants who experienced each specific SOC and PT will be presented. For the

presentation of TEAE incidences, the SOCs will be sorted alphabetically, and within SOC, the preferred term (PT) will be used and presented by decreasing total frequency.

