3.15.1.5 Adverse Event Summaries

The following are the set of adverse event summaries.

- Overall summary of TEAEs
- Incidence of TEAEs by SOC and PT
- Incidence of TEAEs by SOC, PT, and Severity
- Incidence of TEAEs by SOC, PT, and Related to SYNB1934v1

- E.** Incidence of TEAEs by SOC, PT, and Related to PPI
- F.** Incidence of TEAEs Leading to Drug Interruption by SOC and PT
- G.** Incidence of TEAEs Leading to Dose Reduction by SOC and PT
- H.** Incidence of TEAEs Leading to Drug Discontinuation by SOC and PT
- I.** Incidence of AESIs by SOC, PT, and Severity
- J.** Incidence of Serious Adverse Events by SOC and PT
- K.** Incidence of SYNB1934v1 Related Serious Adverse Events by SOC and PT
- L.** Incidence of PPI Related Serious Adverse Events by SOC and PT.

For the DEP only:

- M.** Incidence of Adverse Events prior to first dose of SYNB1934v1 by SOC and PT by Dose Level
- N.** Incidence of Adverse Events prior to first dose of SYNB1934v1 which are PPI related by SOC and PT by Dose Level
- O.** Incidence of TEAEs by SOC and PT by Dose Level
- P.** Incidence of TEAEs by SOC, PT, and Severity by Dose Ramp Period
- Q.** Incidence of TEAEs by SOC, PT, and Related to SYNB1934 by Dose Ramp Period.

This set of analyses will be performed for each of the 3 study periods (DEP, RWP, OLE) separately using the corresponding SAS. The following conventions will be applied:

- For the DEP, the AEs summaries will be presented by SYNB1934v1 dose group and overall. The SYNB1934v1 dose group will be determined by the dose the participant was on at the TEAE start date
- For the RWP, the AEs summaries will be presented by SYNB1934v1 (i.e., each individual iTD dose and overall) and placebo and within these 2 treatment groups by: responder, nonresponder, and overall
- For the OLE, the AE summaries will be presented by responder, nonresponder, and overall. The SYNB1934v1 dose group will be determined by the dose the participant was on at the TEAE start date.

For the presentation of TEAE incidences, the SOCs will be sorted alphabetically, and within SOC, the PT will be used and presented by decreasing total frequency based on the total population.

For the overall summary of TEAEs (i.e., item **A** above), the following information will be provided:

- Number and percent of participants with a TEAE
- Number and percent of participants with a TEAE of Grade 1

- Number and percent of participants with a TEAE of Grade 2

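### Dose-escalation GI bother scores are grouped by final iTD instead of dose at event onset, so events that force a step back are tabulated under a lower dose; the Screening bother summary is restricted to TEAEs

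*SAP*

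**What the plan says.** SAP 3.15.1.8 (GI Daily Diary Card) takes a 0–10 participant rating of how bothersome each GI event was and summarises it for events recorded as AEs. For the dose-escalation period (DEP) the rule is "For GI TEAEs with a start date in the DEP, the tolerability will be summarized by PT and overall, for each iTD and overall".

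SAP 2.2 describes the "iTD, which is defined as the highest dose the participant is able to tolerate". On de-escalation it adds: "In this case, the participant will restart 3 weeks at the lower level iTD". Protocol 3.2 agrees that "this previously tolerated dose will be the iTD", and it bars re-escalation during Part 1.

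The rest of the safety analysis attributes events differently. Protocol 8.10 has safety parameters "summarized descriptively by the treatment regimen (dose and frequency) that the participant was on at the time" of the measurement. SAP 3.15.1.5 says: "The SYNB1934v1 dose group will be determined by the dose the participant was on at the TEAE start date". SAP 3.15.1.6 (dose-ramp tables) and 3.15.1.7 (cross-period tables) follow the same principle.

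The Screening bullet of SAP 3.15.1.8 opens "For GI TEAEs with a start date in the Screening Period". SAP 3.15.1 defines the term: "Treatment emergent adverse events (TEAEs) are any adverse events occurring or worsening in severity after the first administration of SYNB1934v1 study medication".

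**The concern.** The iTD is decided by how well the participant tolerated the drug. Grouping tolerability scores by iTD therefore groups an outcome by a consequence of that outcome. The protocol's grounds for calling a dose intolerable are Grade 3 or worse TEAEs and Grade 2 GI AEs that do not improve. Any of these that are GI events are what the diary scores, so the most informative scores are the ones moved to another row.

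Protocol 1.6 says dosing is limited by GI tolerability, and SAP Table 1 lists safety and tolerability as a DEP objective. A bother table whose dose pattern disagrees with the neighbouring AE tables for reasons of bookkeeping would be hard to interpret and easy to misread.

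The Screening bullet is a separate, smaller problem. It appears meant to give a pre-drug reference, including the PPI run-in from Day -7, but a summary limited to TEAEs cannot do so.

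**Working it through.** The plan gives no target figure for the bother scores, so there is none to reproduce. The attribution follows from the text. Only the direction of the distortion needs an illustration.

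**Attribution, from the rules alone**

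1. A participant tolerates 3×10^11, escalates to 6×10^11, has an intolerable GI event and steps back. The iTD is 3×10^11, so the event is tabulated under 3×10^11. By dose at onset it belongs under 6×10^11.
2. The same happens one level up: an event at 1×10^12 that forces a step back is tabulated under 6×10^11. Re-escalation is barred in Part 1, so no such event can return to the 1×10^12 row.
3. The 1×10^12 row holds only participants who tolerated that dose for 3 weeks, and it pools their events at all three doses.
4. A participant who never tolerates 3 weeks at any dose has no iTD and appears only in the overall row.

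**Illustration (every input is an assumption)**

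- 100 participants; 10%, 20% and 30% of those starting doses 1, 2 and 3 find the dose intolerable.
- One GI event per participant per dose step, plus one tolerated event after a step back.
- Tolerated events score t1 = t2 = t3 = 3; intolerable events score b = 8.

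Participants:
- No iTD: 100 × 0.10 = 10.
- iTD 3×10^11: 90 × 0.20 = 18.
- iTD 6×10^11: 72 × 0.30 = 21.6.
- iTD 1×10^12: 72 × 0.70 = 50.4.

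Mean bother by iTD:
- 3×10^11: (2·t1 + b)/3 = 14/3 = 4.67.
- 6×10^11: (t1 + 2·t2 + b)/4 = 17/4 = 4.25.
- 1×10^12: (t1 + t2 + t3)/3 = 9/3 = 3.00.
- No iTD: 8.0, shown in no iTD row.

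Mean bother by dose at onset:
- 3×10^11: (10×8 + 36×3 + 21.6×3 + 50.4×3)/118 = 404/118 = 3.42.
- 6×10^11: (18×8 + 43.2×3 + 50.4×3)/111.6 = 424.8/111.6 = 3.81.
- 1×10^12: (21.6×8 + 50.4×3)/72 = 324/72 = 4.50.

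The ranking reverses.

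**How far the direction can be trusted**

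In this set-up the iTD means depend only on the scores, not on the intolerance rates. The top row is strictly lowest only if t2 + t3 < t1 + b and t1 + 4·t3 < 2·t2 + 3·b. With tolerated scores of 1, 3, 6 and b = 8, the first condition fails (9 against 9). The iTD means are then 3.33/3.75/3.33, while the onset-dose means at the first set of rates are 1.59/3.81/6.60.

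A grid of 1,200 assumed scenarios used intolerance of 5–20%, 10–40% and 10–50% at the three doses, tolerated scores from flat to steeply rising, and intolerable scores of 6–9:

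| Result | Scenarios | Share |
|---|---|---|
| Top dose strictly lowest by iTD | 900 | 75% |
| Top dose worst or joint worst by onset dose | 1,064 | 89% |
| Both | 764 | 64% |

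These are shares of a chosen grid, not probabilities.

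**Screening bullet**

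Screening ends before the first dose. An event that starts then is a TEAE only if it worsens after dosing and keeps its Screening start date on one record. GI events confined to the pre-dose period are excluded.

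**The case against.** The strongest reply is that little depends on this table. SAP Table 1 gives the safety endpoints as AE incidence and severity, laboratory changes and vital signs; bother score is not among those visible. SAP 3.15.1.5 tabulates TEAE incidence, severity, dose reduction and discontinuation by dose at onset, and 3.15.1.6 adds incidence, dose reduction and discontinuation by dose-ramp day. Events that force a step back are therefore shown under the dose being taken in the dose-reduction table. No test, DMC criterion or stopping rule uses the bother score. All of this stands, and it limits the point to a descriptive score.

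Other parts of the reply also stand:

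- The RWP bullet of SAP 3.15.1.8 also splits by iTD and is sound. Doses cannot be modified in the RWP (Protocol 3.2.2), so in the active arm the iTD is the assigned dose, and placebo is a concurrent comparator. The DEP table is not the only participant-rated summary.
- Protocol 3.2 also allows reduced frequency or skipped doses. Bothersome events at 1×10^12 handled that way stay in the 1×10^12 row if the participant goes on to tolerate the dose.
- Incidence of AEs before the first dose, and of the PPI-related subset, survives as items M and N of SAP 3.15.1.5. What is missing is their bother scores.
- The table shells are in a separate document (SAP 3.19) that cannot be checked here.

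One defence fails. Reading iTD loosely as dose level is not supported: SAP 3.14.1.3 lists an analysis by iTD and a separate MMRM by dose level, so the SAP uses the terms for different things. A programmer following 3.15.1.8 would use the final iTD.

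**Conclusion.** The point holds for the DEP bother summary. As written, it assigns every GI event that forces a step back to a dose below the one being taken and leaves participants without an iTD out of the dose rows. It departs from Protocol 8.10 and SAP 3.15.1.5 to 3.15.1.7, and SAP 3.20 does not declare the departure. This conclusion rests on the definitions and needs no simulation.

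A reader might go further and infer that the top dose must look best tolerated. The documents do not establish that: they give no event counts or expected scores, and the direction depends on assumed inputs. It is likely, but it fails when the scores of tolerated events rise steeply with dose.

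A reader might also infer that the Screening table is empty by definition. It is empty or nearly so, because an event that worsens after dosing can qualify. Nor is the pre-drug reference lost altogether, since incidence is still tabulated.

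No efficacy result is touched. The correction should be made because a stated rule misattributes scores for the toxicity that limits dose, and it is cheap to put right.

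**What to change.** In SAP 3.15.1.8:

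1. DEP bullet: summarise bother scores by preferred term and overall, by the dose level the participant was on at the event start date, and overall. If the by-iTD display is kept, label it supplementary and add a row for participants who reached no iTD.
2. Screening bullet: replace GI TEAEs with *GI AEs with onset before first dose*, in line with items M and N of SAP 3.15.1.5.
3. RWP bullet: leave as it is.

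The cost is two sentences of SAP text and one table shell. Dose at onset is already derived for the other AE tables, and no new data are needed.

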## 1.7. Benefit-Risk Assessment

SYNB1934 and its closely related strain SYNB1618 have been studied in more than 230 HVs and PKU participants. The safety profile has been consistent with the probiotic chassis EcN, which has been used in participants for decades in the European Union and Canada without requirement for prescription. There have been no treatment-related SAEs, no deaths, no systemic toxicity, and no infections. Interindividual variability in tolerability has been observed. The majority of TEAEs have been either mild or moderate in severity and reversible. Most AEs have been GI-related and included GI discomfort, nausea, and vomiting. At increasing doses, GI-related AEs, mainly nausea and vomiting, have been dose limiting. A small dose-related and reversible increase in CRP has been observed in some participants; the clinical significance of this finding is unclear. The CRP level has returned to normal after end of dosing.

Consistent with the design of SYNB1934, clearance is rapid following discontinuation of dosing. In study SYNB1618-CP-001, SYNB1618 was cleared within 4 days following the last dose, as indicated by fecal quantitative polymerase chain reaction (qPCR) analyses. Data from study SYNB1618-CP-002 are consistent. Across all study parts, following up to 7 days of repeat dosing with SYNB1618, no fecal sample was above the limit of quantification at 7 days after last dose. In neither study was there any evidence of colonization, nor did any participant require antibiotic treatment to achieve clearance. Clearance data for SYNB1934 are consistent with that for SYNB1618 with no subject having a positive qPCR sample more than 1 week after the last dose.

Data from completed studies demonstrates that SYNB1934 can access Phe from within the GI tract, as demonstrated by the D5-Phe meal challenge. A dose-related decrease in plasma D5-Phe AUC has been observed, with corresponding increase in strain-specific biomarkers plasma D5-TCA and urinary D5-HA. In the Phase 2 study SYNB1618-CP-003, SYNB1934 led to a mean 34% decrease in plasma Phe in PKU participants, thus demonstrating potential for clinical benefit in the treatment of PKU. Individual variability in Phe lowering was observed. Data from HVs in SYNB1934-CP-001 demonstrate increased Phe conversion capacity of SYNB1934 compared to SYNB1618 based on strain-specific biomarkers.

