3.1.2 Reporting of Numerical Values

All clinical study data will be presented in data listings. Continuous variables will be summarized using the number of observations, mean, standard deviation (SD), median, minimum, and maximum.

Categorical and ordinal variables will be summarized using frequency counts and percentages.

Confidence intervals (CIs) will also be provided where appropriate.

Means, medians, and CIs will be reported to one decimal place more than the data reported on the electronic case report form (eCRF) or by the laboratory/vendor; standard deviations (SD) to two more places. Minimum and maximum will be reported to the same number of decimal places displayed on the eCRF or by the laboratory/vendor. P-values will be two-sided and reported to 4 decimal places.

Proportions will be presented as percentages.

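### The by-arm GI bother table for the RWP covers only recorded GI TEAEs, so it is conditional on having an event and can be misread as a comparison of randomised arms

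*SAP*

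**What the plan says.** Under SAP 3.15.1.8 the diary asks "how much did this event bother you", answered from 0 to 10, so a rating exists only where there is an event. Entry to the summary depends on the investigator: "When the investigator records this event as an AE, the following summaries of the tolerability will be performed". A diary entry judged not to be an AE is left out: "the corresponding GI Daily Diary card entry, including the bothersomeness data, will not be recorded in the adverse event database". Each AE contributes one score: "For AEs occurring over multiple days, the highest bothersomeness score will be recorded".

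For the randomised period the plan is: "For GI TEAEs with a start date in the RWP, the tolerability will be summarized by PT and overall, for treatment group". For the dose-escalation period it is: "For GI TEAEs with a start date in the DEP, the tolerability will be summarized by PT and overall, for each iTD and overall".

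The section does not say whether the unit is the event or the participant. It names no denominator of all dosed participants and gives no value to a participant without a GI event. The general rules do not fill these gaps. SAP 3.1.2 sets the default statistics: "Continuous variables will be summarized using the number of observations, mean, standard deviation (SD), median, minimum, and maximum". SAP 3.4 leaves missing values unimputed unless stated otherwise. By contrast, SAP 3.15.1.6, on AEs by dose ramp day, uses everyone dosed in the period as its denominator.

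**The concern.** Whether a participant has a GI event in the RWP is an outcome that treatment can change. A summary restricted to those events compares subsets selected after randomisation. Participants with no event, who are the best tolerability result, contribute nothing to the score.

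This matters because the summary is presented as tolerability and concerns the drug's main known limitation. Protocol 1.7 says: "At increasing doses, GI-related AEs, mainly nausea and vomiting, have been dose limiting". The RWP is the only placebo-controlled part of the study, so it gives the only randomised comparison of bother. If active drug adds mild events, those events lower the active mean while the total burden rises, and a reader could take the lower mean as better tolerability.

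The problem does not depend on which dose an event is assigned to. It remains when every event is placed in the correct arm.

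**Working it through.** The documents give no expected rate or score for bother, so there is no planned figure to reproduce. All inputs below are assumed. They test the mechanism and do not predict results.

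**1. Two summaries of the same data.** Let p be the proportion of an arm with a GI event and m the mean score among those affected, with one score per affected participant. The conditional mean is m. The mean over all participants, with 0 for no event, is p × m.

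- Active, p = 0.40 and m = 3: conditional mean 3; all participants 0.40 × 3 = 1.2.
- Placebo, p = 0.10 and m = 5: conditional mean 5; all participants 0.10 × 5 = 0.5.

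The order reverses.

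**2. When it reverses.** Active looks better on the conditional mean but is worse per participant when m(active) < m(placebo) and p(active) × m(active) > p(placebo) × m(placebo). Above, 3 < 5 and 1.2 > 0.5. If m is equal in both arms, the conditional means tie whatever the event rates.

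**3. Adding only mild events.** Take 30 participants and 3 events scored 5, then add events scored 2.

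| Extra events | Mean per event | Summed score per participant |
|---|---|---|
| 0 | 15/3 = 5.00 | 15/30 = 0.50 |
| 3 | 21/6 = 3.50 | 21/30 = 0.70 |
| 9 | 33/12 = 2.75 | 33/30 = 1.10 |
| 27 | 69/30 = 2.30 | 69/30 = 2.30 |
| 45 | 105/48 = 2.19 | 105/30 = 3.50 |

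An arm with all the events of another, plus more mild ones, gets a lower mean per event.

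**4. A range.** Three settings for arm A (80% affected with score 2; 60% with score 2; 60% with score 3) were crossed with three for arm B (10% with score 5; 20% with score 4; 20% with score 3). The all-participant mean was 1.2 to 1.8 for A and 0.5 to 0.8 for B. The conditional mean was lower for A in eight of the nine combinations and tied in the ninth (3 versus 3).

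**5. A case without reversal.** Suppose frequency and severity rise together, with 30 per arm. In one arm, 21 participants have two events scored 2 and 3 have two events scored 6. In the other, 3 participants have one event scored 2. The event means are 120/48 = 2.5 and 6/3 = 2.0. The all-participant means of the worst score are 60/30 = 2.0 and 6/30 = 0.2. The direction is right, but the event-based table shows 2.5 versus 2.0 where the per-participant contrast is 2.0 versus 0.2.

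**The case against.** The strongest reply is that GI tolerability by arm is already covered. SAP 3.15.1 and 3.15.1.5 tabulate participants with TEAEs by SOC and PT, by severity, by relatedness, and by interruption, reduction or discontinuation, on the RWP safety analysis set and split by active and placebo. Grade 3 or higher GI events are AESIs. The bother score then answers a narrower, legitimate question: how bothersome an event was, given that it occurred. The default statistics also print the number of observations. All of this stands. A reader might infer that the plan hides the GI event rate; the documents do not support that. Those tables carry no bother score, however, so they cannot supply the participant-level distribution of bother.

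A second reply is that reversal is speculative. Protocol 1.5.1 reports that the number and severity of GI events rose together with dose in healthy volunteers, which would put both summaries in the same direction. That also stands. A reader might infer that the table will favour active drug; the documents give no basis for expecting it, only for saying it can happen.

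A third is that the table is descriptive, with no test attached, and that its shell is in a separate document (SAP 3.19). This is true and limits the weight of the point. Whether the shell uses events or affected participants, the summary remains conditional on an event.

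The last reply is that scoring 0 has its own cost. A zero would cover absence of symptoms, diary entries judged not to be AEs and, unless handled, GI TEAEs with no diary score, since Protocol 5.5.1 also collects AEs by observation and interview. Under the start-date rule, an event that began in the DEP and continues would leave an RWP score of 0. In the DEP, exposure runs from about 3 to 15 weeks, so a maximum score favours shorter exposure, and iTD is itself a tolerability outcome. These objections stand and shape the fix.

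**Conclusion.** The point holds for the RWP. The by-arm bother summary in SAP 3.15.1.8 is conditional on a recorded GI TEAE, omits participants without one, and can rank the arms opposite to the per-participant burden if active-arm events are milder on average than placebo events. In the assumed illustration the contrast moves from 3 versus 5 to 1.2 versus 0.5. With equal scores per event the arms tie, and if severity rises with frequency the direction is preserved but the difference can shrink.

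The consequence is limited to misreading one descriptive table. No test depends on it, and incidence and severity by arm are reported separately. It merits correction because the correction is cheap and no other planned analysis described in the SAP gives a comparison of bother between the randomised arms.

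A reader might infer that the same participant-level score would repair the comparison of dose groups in the DEP. It would not. Groups there are formed by iTD, exposure differs, and an event at a higher dose that was not tolerated is counted under the lower final iTD, whereas SAP 3.15.1.5 uses the dose at onset.

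**What to change.** Amend SAP 3.15.1.8 before the RWP is unblinded.

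- **RWP, existing summary:** keep it, and state that the unit is the event.
- **RWP, addition:** by randomised arm on the RWP safety analysis set, give the number and percent of participants with any GI TEAE. Also give each participant's worst GI bother score in the RWP, with 0 if no GI TEAE was recorded, as a mean and as counts in 0, 1-3, 4-6 and 7-10. SAP 3.5 groups this set by treatment received, so note any participant for whom that differs from the randomised arm.
- **Rules:** count a GI TEAE without a diary score as missing, not 0. State how GI events that began in the DEP and continue into the RWP are handled. Footnote that 0 means no recorded GI TEAE, because diary entries judged not to be AEs are excluded.
- **DEP:** do not compare iTD groups on the zero-filled maximum. Show the number and percent of exposed participants with a GI TEAE beside the event-level scores.

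The data are already collected, and no dose or clinical rule changes. The cost is SAP wording, some programming, a slightly larger table, and a zero category that needs its footnote.
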